15.4 Vital Signs

The following Vital Signs measurements will be reported for this study:

- Heart rate (beats/min)
- Body temperature (°C)
- Respiration rate (breaths/min)
- Systolic blood pressure (mmHg)
- Diastolic blood pressure (mmHg)
- Weight (kg)

The maximum changes of vital sign measurements screening/baseline to maximum changes after start of 1st treatment will be grouped as follows:

Body temperature increase	< 1°C, 1-<2°C, 2-<3°C, ≥ 3 °C
Heart rate increase from baseline <100 beats/min ; ≥ 100 beats/min	≤20 beats/min, >20 – 40 beats/min, >40 beats/min
Heart rate decrease from baseline <100 beats/min; ≥ 100 beats/min	≤20 beats/min, >20 – 40 beats/min, >40 beats/min
SBP increase from baseline <140 mmHg; ≥ 140 mmHg	≤20 mmHg, >20 – 40 mmHg, >40 mmHg
SBP decrease from baseline <140 mmHg; ≥ 140 mmHg,	≤20 mmHg, >20 – 40 mmHg, >40 mmHg
DBP increase from baseline <90 mmHg; ≥ 90 mmHg	≤20 mmHg, >20 – 40 mmHg, >40 mmHg

DBP decrease from baseline <90 mmHg; ≥ 90 mmHg,	≤20 mmHg, >20 – 40 mmHg, >40 mmHg
Respiration rate increase from baseline <20 breaths/min; ≥ 20 breaths/min	≤5 breaths/min, >5 – 10 breaths/min, >10 breaths/min
Respiration rate decrease from baseline <20 breaths/min; ≥ 20 breaths/min	≤5 breaths/min, >5 – 10 breaths/min, >10 breaths/min

Quantitative data will also be examined for trends using descriptive statistics (n, missing, mean, SD, median, Q1, Q3, minimum, and maximum) of actual values, and absolute changes from baseline to each visit.

A listing of vital signs will be prepared in addition. The listing will also include dose level/cohort, subject identifier, vital sign parameter (unit), visit, date/time, value, baseline value, and change from baseline, and flags for potentially clinically meaningful changes. The listing will be sorted by dose level/cohort, subject identifier, vital sign parameter and vital sign measurement date/time.

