24. All SAEs will be documented at each study visit until the 90-day Safety Follow-up Phone Call. After this, all ongoing SAEs must be monitored and followed by the Investigator until stabilization or until the outcome is known, unless the subject is documented as lost to follow-up. Any SAE assessed as related to study drug must be reported whenever it occurs, irrespective of the time elapsed since the last administration of avelumab. At 90 days ( $\pm$  5 days) after the last dose of avelumab, subjects will be contacted by telephone to collect information on new or ongoing SAEs and treatment-related nonserious AEs.
25. Blood samples for PK and ADA will be collected as detailed in [Table 1-3](#).
26. Subjects will be followed every 12 weeks ( $\pm$  7 days) for survival (including assessment of any further anticancer therapy).

**Table 1-2 Schedule of Assessments for Subjects Receiving Avelumab Once a Week for the First 12 Weeks Followed by Once Every 2 Weeks (10 mg/kg Once Weekly Cohort)**

Assessment 	Clinical Screening / Baseline Assessments	Treatment Phase 														Until progression
		≤ Day -14 to Day -1														
		V1	V2	V3	V4	V5	V6	V7	V8	V9	V10	V11	V12	V13	W13 (Roll-over into Once every-2- weeks dosing)	
		W1	W2	W3	W4	W5	W6	W7	W8	W9	W10	W11	W12			
D1	D8	D15	D22	D29	D36	D43	D50	D57	D64	D71	D78	D85				
CCI																
Written informed consent	X															
Inclusion/exclusion criteria	X															
Medical history 	X															
Demographic data	X															
Hepatitis B, hepatitis C and HIV tests	X															
Full physical examination 	X															
Symptom-directed physical exam 		As indicated throughout the Treatment Phase														
Height	X															

Assessment 	Clinical Screening / Baseline Assessments ≤ Day -14 to Day -1	Treatment Phase 													Until progression	
		V1	V2	V3	V4	V5	V6	V7	V8	V9	V10	V11	V12	V13		
		W1	W2	W3	W4	W5	W6	W7	W8	W9	W10	W11	W12	W13 (Roll-over into Once every-2- weeks dosing)		
		D1	D8	D15	D22	D29	D36	D43	D50	D57	D64	D71	D78	D85		
Vital signs	X	X	X	X	X	X	X	X	X	X	X	X	X	X	X	2-weekly
Weight	X	X	X	X	X	X	X	X	X	X	X	X	X	X	X	2-weekly
ECOG PS 	X	X 	X	X	X	X	X	X	X	X	X	X	X	X	X	2-weekly
Enrolment (if eligible) 	X															
12-lead ECG	X	X	X	X	As indicated and decided by Investigator											
Hematology and hemostaseology	X		X	X	X	X	X	X	X	X	X	X	X	X	X	2-weekly

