### 7.1.2 Treatment Phase

The Treatment Phase begins on Cycle 1 Day 1 with the first administration of avelumab and will continue until progression (see Sections 6.2 and 7.3.3), significant clinical deterioration (clinical progression), unacceptable toxicity, or any criterion for withdrawal from the study or IMP occurs

(see Sections 5.5.1 and 5.5.2). However, a subject may remain on avelumab beyond RECIST 1.1-defined disease progression if their ECOG performance status has remained stable, there are no new symptoms or worsening of existing symptoms, and, if in the opinion of the Investigator, the subject will benefit from continued treatment with avelumab (see Section 6.2). For subjects who continue avelumab beyond progression, treatment should be stopped immediately if the subject no longer tolerates avelumab or if therapeutic failure occurs. See Section 6.2.

[figure not shown]
Re-initiation of avelumab may be allowed in a subject who discontinues administration of avelumab but subsequently fails to confirm and verify original PD and meets the Criteria for Continuation of Treatment Beyond Progression (See Section 6.2 and 7.3.3).

Subjects receiving avelumab who have experienced a CR should be treated for a minimum of 12 months, and/or until disease progression or unacceptable toxicity, after confirmation of response.

For subjects receiving avelumab once every 2 weeks, subjects will be asked to visit the study site every 2 weeks during the Treatment Phase. A time window of up to 3 days before or 1 day after the scheduled visit day (- 3/+ 1 days) will be permitted for all study procedures (except PK sampling visits on Days 2 and 3).

For subjects receiving avelumab once weekly, subjects will be asked to visit the study site once weekly for the first 12 weeks, and then once every 2 weeks starting at Week 13 during the Treatment Phase. A time window of 1 day before or 1 day after the scheduled visit day (- 1/+ 1 days) is permitted for all study procedures while subjects receiving avelumab once weekly (12 consecutive weeks). A time window of up to 3 days before or 1 day after the scheduled visit day (- 3/+ 1 days) will be permitted for all study procedures while subjects receiving avelumab once every 2 weeks (Week 13 and thereafter).

CCI

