#### 7.4.4 Vital Signs, Physical Examinations, and Other Assessments

The ECOG performance status (see Section 12, Appendix IV) will be assessed at Clinical Screening and at subsequent visits as indicated in the Schedule of Assessments (Table 1-1 and Table 1-2) and documented in the eCRF, even if the IMP is on hold for the subject. More frequent examination may be performed at the Investigator's discretion, if medically indicated.

Body weight (to the nearest 0.1 kilogram [kg]) will be measured at Clinical Screening and at subsequent visits as indicated in the Schedule of Assessments (Table 1-1 and Table 1-2) and

documented in the eCRF. Body height in centimeters (cm) will be measured at Clinical Screening only.

Physical examination will include an examination of general appearance, skin, neck (including thyroid), eyes, ears, nose, throat, lungs, heart, abdomen, back, lymph nodes, extremities, and a basic nervous system evaluation. A full physical examination will be conducted at Clinical Screening, at the EOT Visit, and at the 30-day Safety Follow-up Visit. At visits during the Treatment Phase (see Schedule of Assessments [Table 1-1 and Table 1-2]), the physical examination will be symptom-directed. Results from the physical examination, including any abnormalities, will be documented in the eCRF. Abnormal findings are to be reassessed at subsequent visits. Details of the physical examination must be present in the source documentation at the study site.

A 12-lead ECG will be performed and recorded at Clinical Screening and as indicated in the Schedule of Assessments (Table 1-1 and Table 1-2). All subjects will have ECG assessment at baseline, and at the first 3 times of study drug treatment after avelumab infusion. In following visits, ECG will be arranged if considered necessary by the Investigator. Electrocardiograms will be performed in the supine position after the subject has been breathing quietly for 5 minutes. The ECG results will be used to evaluate heart rate, atrial-ventricular conduction, QR\* and QT intervals, and possible arrhythmias. Interpretation of the ECG trace must be made by a qualified physician and documented on the ECG eCRF. Each ECG trace should be labeled with the Study Number, Subject Identifier Number, and date, and kept in the source documents at the site.

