### 8.5.3 Analysis of Secondary and Safety Endpoints

#### 8.5.3.1 Analysis of Safety Endpoints

The extent of exposure to avelumab will be characterized by duration (weeks), number of administrations, cumulative dose (mg/kg), dose intensity (mg/kg/week), relative dose intensity (actual dose given/planned dose), number of dose reductions, and number of dose delays.

Safety analyses will be performed on the Safety Analysis Set. The safety endpoints will be tabulated by dose level and cohort, using descriptive statistics.

Safety assessments will be based on review of the incidence of AEs, ADRs, and changes in vital signs, ECGs, body weight, and laboratory values (hematology and serum chemistry).

The on treatment period is defined as the time from the first administration of avelumab to the last administration of avelumab date plus 30 days or the earliest date of subsequent anticancer drug therapy minus 1 day, whichever occurs first.

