15.3 Clinical Laboratory Evaluation

All laboratory assessments are performed at local laboratories and comply with local requirements.

Laboratory values (including corresponding normal ranges) from local laboratories will be converted into the standard units by data management. The results in standard units will be used for the analyses.

Laboratory results will be classified according to the NCI-CTCAE toxicity grading version 4.03. If toxicities for high and low values of a specific parameter are defined, these toxicities will be analyzed separately for the parameter as “Parameter low” and “Parameter high” (appendix 18.3).

Laboratory results that are not part of the NCI-CTCAE will be presented according to the categories: below normal limits, within normal limits and above normal limits (according to the local laboratories normal ranges).

- **Hematology:** Hematocrit, Hemoglobin, Platelet count, Red blood cells (RBC) count, White Blood Cell Count, Absolute lymphocytes count, Lymphocytes, Absolute Neutrophils count, Neutrophils, Absolute monocyte count, Monocytes, Absolute eosinophil count, Eosinophils, Absolute basophil count, Basophils, RBC morphology, Absolute reticulocytes count, Reticulocytes, Mean corpuscular hemoglobin (MCH), Mean corpuscular volume (MCV), Mean corpuscular hemoglobin concentration (MCHC).
- **Hemostaseology:** Activated partial thromboplastin time (aPTT), Prothrombin time (PT), International Normalized Ratio (INR).
- **Biochemistry:** Albumin, Alkaline phosphatase, Alanine Aminotransferase (ALT), Amylase, Aspartate Aminotransferase (AST), Gamma Glutamyl Transpeptidase (GGT), Blood Urea Nitrogen (BUN), Urea, Calcium, Chloride, Cholesterol, Creatine kinase, Creatinine, C-Reactive Protein (CRP), Glucose, Lactate dehydrogenase (LDH), Lipase, Phosphorus, Magnesium, Potassium, Sodium, Total bilirubin, Protein total, Uric acid, Triglycerides, Hemoglobin A1c.
- **Hormonal tests:** Free Thyroxine (T4), Thyroid-Stimulating Hormone (TSH), Follicle-stimulating hormone.
- **Urinalysis:** pH, Specific gravity, Protein content, Sediment analysis, Albumin, Immunoglobulin G.

NCI-CTCAE grades available:

The laboratory toxicities will be tabulated by the worst on-treatment CTCAE grade or the shift of CTCAE grade from baseline to worst grade during on-treatment period using descriptive statistics (count and percentage). The highest CTCAE grade during the on-treatment period is considered as the worst grade for the summary.

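### Worst-value tables for vital signs, ECOG, hematology and core chemistry are not like-for-like between the weekly and 2-weekly cohorts (12 versus 6 scheduled assessments through Day 85)

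*SAP*

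**What the plan says.** **Summaries.** SAP 15.4 on vital signs: "The maximum changes of vital sign measurements screening/baseline to maximum changes after start of 1st treatment will be grouped as follows". SAP 15.3 on laboratory data: "The highest CTCAE grade during the on-treatment period is considered as the worst grade for the summary". Analytes without a CTCAE grade are handled the same way, as shifts to above or below normal at any time on treatment. SAP 15.5.2 tabulates the shift from baseline to worst on-treatment ECOG status by dose level/cohort. Protocol 8.5.3.1 sets the layout: "The safety endpoints will be tabulated by dose level and cohort, using descriptive statistics". SAP 13.2 repeats it.

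**Schedules.** Under Protocol 7.1.2, in the 2-weekly cohorts "subjects will be asked to visit the study site every 2 weeks during the Treatment Phase". In the weekly cohort "subjects will be asked to visit the study site once weekly for the first 12 weeks", and every 2 weeks from Week 13. Protocol 7.4.4 says ECOG "will be assessed at Clinical Screening and at subsequent visits as indicated in the Schedule of Assessments", and Tables 1-1 and 1-2 place it at every visit. The same tables place vital signs at every visit, and hematology and either core or full chemistry at every visit after Day 1.

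**By-visit summaries.** SAP 15.3 and 15.4 also plan descriptive statistics of values and changes from baseline at each visit. SAP 15.5.2 plans only the worst-status shift table and a listing for ECOG.

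Nothing limits the worst-value tables to days shared by all cohorts or asks for the number of assessments behind each subject's worst value.

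**The concern.** A maximum can only rise as more values enter it. Two subjects with the same underlying behaviour and the same time on study will differ in expected worst value if one is measured twice as often.

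This matters because the weekly cohort exists to assess the safety of an established dose given more often (Protocol 5.1.1.1), so readers will set its column beside the 2-weekly columns. It is also outside the DLT evaluation, so its safety reading rests on the adverse-event, laboratory, vital-sign and ECOG outputs. In a cohort of 6, one subject moving category is 1/6, about 17 percentage points. A worst-value table cannot show how much of such a difference comes from the regimen and how much from the visit schedule.

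**Working it through.** The documents give no figure for assessments per cohort or for the size of this effect. Cohort sizes are consistent: 3 + 6 + 6 + 6 = 21, or 6 + 6 + 6 + 6 = 24 if the 3 mg/kg cohort is expanded, matching the planned approximately 21, up to 24. The weekly cohort has 6.

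**1. Count the assessments.** A pre-dose Day 1 value counts as baseline (SAP 9.3.2).
- 2-weekly (Table 1-1): Days 15, 29, 43, 57, 71, 85, so 84/14 = 6.
- Weekly (Table 1-2): Days 8, 15, 22, ... 85, so 84/7 = 12.
- Core chemistry analytes, which are also measured at full-panel visits: 4 core + 2 full = 6 versus 10 core + 2 full = 12.
- Analytes in the full panel only: Days 43 and 85 in every cohort, so 2 versus 2.

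Of the 19 CTCAE-graded chemistry parameters in SAP 15.3, 11 are core. The other 8 are full-panel only: GGT, lipase, amylase, albumin, uric acid, cholesterol, creatine kinase and triglycerides. With the 5 graded hematology parameters, 5 + 11 = 16 of 24 graded parameters have unequal schedules.

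**2. Maximum systolic increase above 20 mmHg, no true cohort difference, through Day 85.** Each visit's change is its value minus baseline, with normal errors, and the maximum is taken over 6 or 12 visits. The SD and correlation are assumptions, and the probabilities come from simulation.

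| Assumed SD | Correlation between weeks | 2-weekly (6) | Weekly (12) |
|---|---|---|---|
| 8 mmHg | independent | 15% | 22% |
| 10 mmHg | independent | 27% | 37% |
| 12 mmHg | independent | 37% | 48% |
| 10 mmHg | AR(1) 0.5 | 24% | 31% |
| 10 mmHg | AR(1) 0.8 | 16% | 19% |

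In 6 subjects at SD 10 mmHg, the expected excess is 6 × (0.37 − 0.27) = 0.6 of a subject with independent visits and 6 × (0.19 − 0.16) ≈ 0.2 at AR(1) 0.8.

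**3. Any category limit (laboratory grade, ECOG).** With an assumed crossing probability p per assessment and independent visits, P(at least one crossing) = 1 − (1 − p)^k.
- p = 1%: 1 − 0.99^6 = 5.9% versus 1 − 0.99^12 = 11.4%.
- p = 5%: 1 − 0.95^6 = 26.5% versus 1 − 0.95^12 = 46.0%.

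Within-subject correlation shrinks this. Over Weeks 1 to 12 only (5 versus 11 assessments) at p = 5%, independence gives 22.6% versus 43.1%. A common correlation of 0.5 gives 16.7% versus 26.0%, 0.8 gives 11.6% versus 15.7%, and 0.95 gives 8.1% versus 9.6%.

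**4. Longer follow-up.** The planned tables do not stop at Day 85. The weekly cohort opens only after 20 mg/kg is judged safe, and the primary cutoff is Week 13 of the last subject (Protocol 8.6), so earlier 2-weekly subjects can be followed longer. A 2-weekly subject treated to Day 169 has 168/14 = 12 post-baseline visits, the same as a weekly subject at Day 85. At SD 10 mmHg, the 2-weekly subject at Day 169 versus the weekly subject at Day 85 gives:
- independent visits: 37% versus 37%;
- AR(1) 0.5: 35% versus 31%;
- AR(1) 0.8: 27% versus 19%.

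At equal follow-up the ratio of counts falls with time: 12/6 = 2.0 at Week 13, 18/12 = 1.5 at Week 25 and 30/24 = 1.25 at Week 49.

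**5. After restriction.** On the six shared days both cohorts have k = 6, so in these models the schedule-driven gap is zero.

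**The case against.** **The tables are descriptive.** This stands: no between-cohort test or contrast is planned and the sample size has no statistical basis. Side-by-side columns will still be read against each other.

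**By-visit summaries already answer it.** They do for laboratory values and vital signs, which can be read on Days 15 to 85 free of this effect. They do not repair the worst-grade, shift and maximum-change tables, and ECOG has no by-visit summary.

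**The effect is small and rests on assumptions.** This stands: at high correlation it is a fraction of one subject. Protocol 7.4.3 also repeats clinically significant new laboratory abnormalities weekly in every cohort, which narrows the gap once something has been seen. It does not help with an abnormality that comes and goes between 2-weekly visits.

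**More visits partly reflect more infusions, the exposure under study.** True, but the worst-value tables cannot separate a real regimen effect from the schedule effect.

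**Shared days are not perfectly matched either.** This stands: they fall 7 days after the last dose in the weekly cohort and 14 in the others.

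A reader might infer that the weekly cohort must look more toxic in these tables. The documents do not support that. Step 4 shows that follow-up can offset or reverse the effect, and the documents do not give time on treatment. Even at equal follow-up it is a shift in expectation. In 6 versus 6 subjects (Weeks 1 to 12, p = 5%) the weekly count is higher in 68% of simulated trials with independent visits and 40% at correlation 0.8, and lower in 14% and 25%.

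**Conclusion.** The worst-value tables for vital signs, ECOG, hematology and core chemistry are not like-for-like between the weekly and 2-weekly cohorts. The 12 versus 6 count through Day 85 comes directly from the schedules. Full-panel-only chemistry is unaffected, so the point does not extend to all laboratory data.

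At equal time on study, the weekly cohort's expected worst value is raised whenever repeat values are less than perfectly correlated. For the systolic example at an assumed SD of 10 mmHg, the excess is 3 to 10 percentage points across the correlations examined. For the full on-treatment tables as planned, the net direction is unknown. The consequence is confined to descriptive secondary safety tables; the DLT and PK primary endpoints are unaffected.

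**What to change.** Keep the all-values tables in SAP 15.3, 15.4 and 15.5.2 as the main safety display, so that no extreme value is lost. Then:
- Add a supplementary version of the worst-grade and shift tables (hematology and core chemistry), the maximum-change table (vital signs) and the worst-ECOG table, restricted to scheduled assessments on Days 15, 29, 43, 57, 71 and 85 within the protocol visit windows. Ending at Day 85 also removes most of the follow-up imbalance.
- Report the number of assessments per subject by cohort, since early discontinuation can still leave the counts unequal.
- State that any weekly versus 2-weekly reading of these measures rests on the supplementary version.

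The cost is a few lines of SAP text and one visit-filtered rerun of existing tables. The supplementary version omits weekly-only days such as 8 and 22 and unscheduled values, and its shared days differ in time since last dose (7 versus 14 days). Both limits should be footnoted.

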15.5 Other Safety or Tolerability Evaluations

15.5.1 ECG

A shift table from baseline to the worst on-treatment conclusion will be tabulated with the subsequent categories:

- Normal ECG
- Abnormal ECG
 - ECG abnormalities non-clinically significant
 - ECG abnormalities clinically significant
- Missing
- Overall

Conclusions are sorted as Normal/Abnormal non-clinically significant/Abnormal clinically significant, the latest one being considered as the worst. If no post-baseline data are available the worst on-treatment result will be accounted as missing. If significance is not provided, the conclusion will be classified as “Abnormal ECG”. This “Abnormal ECG” category will count abnormal conclusion with missing significance only.

Quantitative data will also be examined for trends using descriptive statistics (n, missing, mean, SD, median, Q1, Q3, minimum, and maximum) of actual values and absolute changes from baseline to each visit.

A listing of ECG values will be provided with all information included from the ECG where the abnormality was observed.

15.5.2 Eastern Cooperative Oncology Group/ ECOG Performance Status

Shifts in ECOG performance status from baseline to worst on-treatment performance status will be summarized by dose level/cohort. Missing category will also be included.

A listing will also be provided for ECOG performance status.

16 Analyses of Other Endpoints

16.1 Pharmacokinetics

Serum concentrations and PK parameters will be listed by dose level, study day, and/or scheduled time point, as appropriate, and summarized using descriptive statistics as described in Section **Error! Reference source not found.**

Graphical displays of individual and mean (\pm SD for linear profiles only) serum concentration-time profiles will be presented on linear and semi-logarithmic scales by dose level up to 336 hours post-dose for the bi-weekly cohorts. Mean (\pm SD, linear profiles only) trough serum concentration-time profiles will be prepared for the once-weekly and bi-weekly cohorts. Individual serum concentration-time profiles will be presented on linear scale by study day for the once-weekly cohort.

For the PK analysis, pre-dose sample concentrations that are below the limit of quantification (BLQ) will be assigned a numerical value of zero for the calculation of AUC. On Day 1, any missing pre-dose value will also be assigned a numerical value of zero for the calculation of AUC. Any anomalous concentration values observed at pre-dose will be used as such in the PK analysis and identified in the CSR. All post-dose BLQ concentrations will be set to 'zero' in all cases.

Noncompartmental computation of PK parameters will be performed for the 3 mg/kg, 10 mg/kg, and 20 mg/kg once every 2 weeks dose escalation cohorts. Pharmacokinetic parameters will be evaluated and listed for all patients who provide sufficient concentration-time data. At least 3 valid, post-dose concentrations will be required in the PK profile to obtain any PK parameter estimate.

Individual PK parameters will be calculated using actual elapsed time from dose with a maximum of 14 significant digits in the time data (or using scheduled time if actual time is not available). The pre-dose sample will be considered as if it had been taken simultaneously with the administration of IMP. For any interim analyses, nominal time from dose will be used to calculate PK parameters.

Partial area $AUC_{0-\tau}$ should be calculated using the scheduled dosing interval, as defined in the CTP. The actual dosing interval calculated from CRF time data should not be used. The following rules apply when calculating the partial area $AUC_{0-\tau}$ within the observed time interval from T_1 to T_2 :

- If the start time of the interval (T_1) occurs before the first observation, the observation at T_1 will be estimated using the linear interpolant between the first data point and C_0 . For single dose data $C_0 = 0$ when the drug was administered via an extravascular route or via infusion, and C_0 is the estimated dosing time intercept when the drug was administered as an IV bolus.
- If either T_1 or T_2 falls within the time range in which samples were taken, but does not coincide with an observed data point, then a linear interpolation is performed to estimate the corresponding concentration value.
- If the end time of the interval (T_2) occurs after the last measurable concentration and the terminal regression (λ_z) is estimable, then λ_z is used to estimate the concentration at T_2 . The linear trapezoidal rule will be used to calculate the area from the last observation time to the end time of the partial area (T_2). If λ_z cannot be estimated the partial area will not be calculated.

For each subject in the PK analysis set the following PK parameters will be calculated for avelumab on Day 1 in the bi-weekly cohorts, if possible:

AUC_{0-t}	The area under the concentration-time curve from time zero (dosing time) to the last sampling time (t_{last}) at which the concentration is at or above the lower limit of quantification. Calculated using the mixed log linear trapezoidal rule (linear up, log down). Units: h* μ g/mL.
AUC_{0-tau}	The area under the serum concentration-time curve from time zero (dosing time) to tau (336 hours), calculated using the mixed log linear trapezoidal rule (linear up, log down). Units: h* μ g/mL.
$AUC_{0-\infty}$	The area under the serum concentration-time curve from time zero (dosing time) extrapolated to infinity, based on the predicted value for the concentration at t_{last} , as estimated using the linear regression from λ_z determination. $AUC_{0-\infty} = AUC_{0-t} + C_{last\ pred} / \lambda_z$. Units: h* μ g/mL.
$AUC_{extra\%}$	The AUC from time t_{last} extrapolated to infinity given as a percentage of $AUC_{0-\infty}$. $AUC_{extra\%} = (\text{extrapolated area} / AUC_{0-\infty}) * 100$. The predicted $AUC_{0-\infty}$ should be used. Units: %.
λ_z	Terminal elimination rate constant, determined from the slope of the regression line of log(concentration) versus time. Units: h ⁻¹ .
C_{max}	Maximum serum concentration observed, obtained directly from the concentration versus time curve. Units: μ g/mL.
C_{last}	Last quantifiable serum concentration observed, obtained directly from the concentration versus time curve. Units: μ g/mL.
C_{trough}	The concentration observed immediately before next dosing. Units: μ g/mL.

t_{\max}	Time to reach maximum serum concentration, obtained directly from the concentration versus time curve. Units: h.
$t_{1/2}$	Terminal elimination half-life, determined as $\ln(2)/\lambda_z$. Units: h.
AUC_{0-t}/dose	Dose-normalized AUC_{0-t} . Actual mg/kg dose administered will be used in the calculation of this parameter. Units: $(h*\mu\text{g/mL})/(\text{mg/kg})$.
$AUC_{0-\tau}/\text{dose}$	Dose-normalized $AUC_{0-\tau}$. Actual mg/kg dose administered will be used in the calculation of this parameter. Units: $(h*\mu\text{g/mL})/(\text{mg/kg})$.
C_{\max}/dose	Dose-normalized C_{\max} . Actual mg/kg dose administered will be used in the calculation of this parameter. Units: $(\mu\text{g/mL})/(\text{mg/kg})$.

The following PK parameters will be calculated for diagnostic purposes and listed, but will not be summarized:

- The time interval (h) of the log-linear regression ($\lambda_{z\text{ low}}, \lambda_{z\text{ upp}}$) to determine λ_z ($t_{1/2}$, Interval).
- Number of data points (N_λ) included in the log-linear regression analysis to determine λ_z .
- Goodness of fit statistic (Rsq) for calculation of λ_z .

The regression analysis should contain data from at least 3 different time points in the terminal phase consistent with the assessment of a straight line on the log-transformed scale. Phoenix WinNonlin best-fit methodology will be used as standard. The last quantifiable concentration should always be included in the regression analysis, while the concentration at t_{\max} and any concentrations <LLOQ which occur after the last quantifiable data point should not be used.

The coefficient of correlation (Rsq) should be ≥ 0.800 and the observation period over which the regression line is estimated should be at least twofold the resulting $t_{1/2}$ itself. If %AUC_{extra} is greater than 20%, the rate constants and all derived parameters (e.g., $t_{1/2}$, $AUC_{0-\infty}$) will be included in the parameter outputs and descriptive statistics but will be flagged and discussed appropriately. Any flags should be included in the study specific SDTM.

Scatter-plots of individual patient data and GeoMean values of C_{\max}/dose , $AUC_{0-\tau}/\text{dose}$, and AUC_{0-t}/dose versus dose will be prepared.

Dose proportionality of PK parameters will be assessed graphically based on exposure data ($AUC_{0-\tau}$ and C_{\max}).

The Phoenix WinNonlin NCA Core Output will be provided in a separate listing.

